9.7.2 Primary objectives

The analysis for the primary study objectives will be conducted separately for each data source. In addition, meta-analysis will be performed to combine the adjusted RRs regarding the primary outcomes (i.e., MCM and select pregnancy loss outcomes) from the individual data sources where comparative analysis are performed as described in Section 9.7.1. The description of the analysis to be conducted for each primary study objective is provided in the following sections.

Objective 1

The analysis to describe and estimate the risk of MCM in live and non-live offspring from the mothers who had moderate/severe SLE and were exposed to anifrolumab during the first trimester of pregnancy or exposed to SOC and unexposed to anifrolumab during the first trimester of pregnancy (study objective 1) will be performed using the *MCM* cohort and its sub-cohorts as defined in Section 9.2.2). The crude and adjusted cumulative incidence (with corresponding 95% CI) of the MCM in live and non-live offspring from the mothers who had moderate/severe SLE and were exposed to anifrolumab during the first trimester of pregnancy or who were exposed to SOC and unexposed to anifrolumab during the first trimester of pregnancy will be estimated separately. The crude cumulative incidence (i.e., risk) will be calculated as the total number of live and non-live offspring with MCM divided by the total number of live and non-live offspring. The adjusted cumulative incidence (i.e., risk) will be estimated following PS adjustment, if suitable for the data. Additionally, the Kaplan-Meier plots will be generated both before and after application of PS adjustment to obtain crude and adjusted estimates for the time from birth to MCM ascertainment, respectively (as described in Section 9.7.1).

Objective 2

To estimate the relative risk of MCM in live and non-live offspring from the mothers who had moderate/severe SLE and were exposed to anifrolumab during the first trimester of pregnancy or exposed to SOC and unexposed to anifrolumab during the first trimester of pregnancy (study objective 2), the crude and adjusted RRs (with corresponding 95% CIs) will be estimated using the *MCM* cohort (as defined in Section 9.2.2). The crude RR and its 95% CI will be estimated using a regression model as specified in Section 9.7.1. The adjusted RR and its 95% CIs will be estimated by using the same regression model after applying an appropriate PS adjustment method

as described in Section 9.7.1. In addition, meta-analysis on the data source specific crude and adjusted RRs of MCM in live and non-live offspring from mothers who were exposed or unexposed to anifrolumab during pregnancy will be conducted as described in Section 9.7.1.

Objective 3

The analysis to describe and estimate the risk of select pregnancy loss outcomes (composite of spontaneous abortion and stillbirth) in all pregnancies from the mothers who had moderate/severe SLE and were exposed or unexposed to anifrolumab during pregnancy (study objective 3) will be performed using the *pregnancy* cohort (as defined in Section 9.2.2). The crude and adjusted cumulative incidence (with corresponding 95% CI) of the select pregnancy loss outcomes (composite of spontaneous abortion and stillbirth) will be estimated for cases where mother was exposed to anifrolumab during pregnancy and for cases where mother was unexposed to anifrolumab during pregnancy. The crude cumulative incidence (i.e., risk) will be calculated as the total number of select pregnancy loss outcomes (composite of spontaneous abortion and stillbirth) divided by the total number of pregnancies. The adjusted cumulative incidence (i.e., risk) will be estimated following PS adjustment, if suitable for the data.

Objective 4

To estimate the relative risk of select pregnancy loss outcomes (composite of spontaneous abortion and stillbirth) in pregnancies from the mothers who had moderate/severe SLE and were exposed or unexposed to anifrolumab during pregnancy (study objective 4), the crude and adjusted RR (with corresponding 95% CI) will be estimated using the *pregnancy* cohort (as defined in Section 9.2.2). The crude RR and its 95% CI will be estimated using a regression model as specified in Section 9.7.1. The adjusted RR and its 95% CI will be estimated using the same regression model following an appropriate PS adjustment method as described in Section 9.7.1.

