Objective	Main features	Input Cohort/ Population	Sub-cohort Abbreviation	Additional criteria to be applied to the input Cohort/ Population
Primary cohort MCM (MCM_exp+MCM_unexp)				

Primary objective 1 & 2;
 
Secondary objective 5a-b
 
Exploratory objective 15
	
Describe and estimate the risk and relative risk of MCM.
 
Describe cohort demographic and clinical characteristics.
 
Among live and non-live offspring
	Exposed study population	MCM_exp	
INCLUSION:
 
 • MCM: Pregnancies exposed to anifrolumab during the first trimester of pregnancy (+16 weeks prior to LMP2) • All pregnancies ending in spontaneous abortion, elective termination of pregnancy and stillbirth, regardless of linkage mother-offspring within the study period • Pregnancies with linkage mother-offspring within the study time period 
EXCLUSION:
 
 • Adopted children (where information is available)

Primary objective 1 & 2;
 
Secondary objective 5a-b
 
Exploratory objective 15
	
Describe and estimate risk and relative risk of MCM.
 
Describe cohort demographic and clinical characteristics.
 
Among live and non-live offspring
	Unexposed study population	MCM_unexp	
INCLUSION:
 
 • All pregnancies ending in spontaneous abortion, elective termination of pregnancy and stillbirth, regardless of linkage mother-offspring within the study period • Pregnancies with linkage mother-offspring within the study time period 
EXCLUSION:
 
 • Pregnancies exposed to anifrolumab during the first trimester (+16 weeks prior to LMP2) (see Section 9.3.1) • Adopted children (where available)

Objective	Main features	Input Cohort/ Population	Sub-cohort Abbreviation	Additional criteria to be applied to the input Cohort/ Population
Secondary cohort mCM (mCM_exp+mCM_unexp)				

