9.3.2 Outcome definition and measures

In line with the study objectives (see Section 8.1), the study’s primary, secondary and exploratory outcomes are defined below. Study outcomes will be identified based on the coding system used in the data sources (ICD-10 CM for the USA data sources, ICD-10 for Denmark, Finland and France; MedDRA codes for Germany). ICD-10 codes are provided in [Appendix D. Exemplar Codelists](#).

The maternal death rate in women with SLE as well as the infant death rate of women with SLE are reported to be low and thus, the maternal and infant death rates are expected to be low in this study (21, 99).

Primary outcomes

During the outcome ascertainment period, which will span from the index date to the exit date for each offspring, outcome events will be identified in registers and data sources using ICD-10 or equivalent codes (ICD-10 CM for the USA data sources, ICD-10 for Denmark, Finland, and France; MedDRA codes for Germany). For the primary outcome the **index date/start of follow-up**, included in the enrolment, will be defined as the LMP2 (as defined in Section 9.1) from which the foetus/offspring will be followed up for the outcome of interest. The **exit date/end of follow-up** will be defined as the first of the following: end of the study period, death, emigration (where available), loss to follow-up (disenrollment/de-registering), reaching the age of 1 year or date of first diagnosis of the outcome at study.

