For the select pregnancy loss outcomes, the **index date/start of follow-up**, will be defined as the LMP2 (as defined in Section 9.1) from which the pregnancy will be followed until the outcome of interest. The **exit date/end of follow-up**¹¹ will be defined as the end of the study period, death, emigration (where available), loss to follow-up (disenrollment/de-registering), or date of first diagnosis of the outcome at study, or delivery, whichever is the earliest.

The select pregnancy loss outcomes will be defined as the presence of at least one of the following criteria:

- ICD-10 code of spontaneous abortion¹² (unintended loss of an intrauterine pregnancy) which is less than 22 weeks of gestation for the European data sources (40); less than 20 weeks for the USA data sources (64);
- ICD-10 code of stillbirth¹³ (unintended foetal death occurring at or after 22 weeks of gestation for the European data sources (78); at or after 20 weeks for the USA data sources (64).

Secondary outcomes

During the outcome ascertainment period, outcome events will be identified based on ICD-10 CM codes for the USA, ICD-10 for Denmark, Finland and France; MedDRA codes for Germany recorded in patient registries.

Minor congenital malformations

For this outcome the **index date/start of follow-up**, will be defined as the LMP2 (as defined in Section 9.1) from which the foetus/offspring will be followed up for the outcome of interest. The **exit date/end of follow-up** will be defined as the end of the study period, death, emigration (where available), loss to follow-up (disenrollment/de-registering), reaching the age of 1 year or date of first diagnosis of the outcome at study, whichever is the soonest.

¹¹ Specific outcome censoring rules will be applied. For spontaneous abortion outcome specific end of follow-up will be 22 weeks of gestation for the European data sources or 20 weeks for the USA data sources further details will be specified in the SAP.

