USA (DAPI)	2007	4% ¹⁰	223	3-6	Available	Available	Available	Available	Available	Partial: - May be extracted from medical records for subset of patients	- Ability to capture anifrolumab exposure and primary outcomes - Number of pregnancies captured

Abbreviation used in the table: NA, Not available; CM, Congenital malformation; SOC, Standard of care; SLE, Systemic lupus erythematosus; UK, United Kingdom; USA, United States of America; MCM, Major congenital malformation; mCM, minor congenital malformation; ICD-10 GM, International Classification of Diseases 10th Revision German Modification; SGA, Small for gestational age; DCIR, Données de Consommation Inter-Régimes; PMSI, Programme de médicalisation des systèmes d'information

¹ Estimates for the annual number of pregnancies in women with SLE was directly provided by Carelon Research, DAPI and RHEKISS. For the other data sources, an estimate for the annual number of pregnancies in women with SLE was computed (see Section 9.5.1).

² Exposure to anifrolumab was based on the availability/information of biologics (in general) and belimumab (Benlysta) as a proxy for utilisation of anifrolumab.

³ Refers to major and minor congenital malformations.

⁴ Refers to ectopic pregnancy, spontaneous abortion, elective termination of pregnancy, stillbirth, infections requiring hospitalisation during pregnancy, and caesarean section.

⁵ Refers to preterm birth and small for gestational age.

⁶ Varies by the component registers.

⁷ Only high-cost hospital administered drugs are captured in SNDS. Therefore, exposure to anifrolumab can only be captured provided it is among the list of high-cost drugs.

⁸ RHEKISS is a nationwide, multi-centre registry for pregnancies in rheumatology and includes rheumatologist and patient reported data in the form of electronic case reports. As of July 2022, the registry includes 1907 patients (about 270 patients per year from 2015 onwards).

⁹ Approximately 20% of USA population (75 million) have ever been recorded by Carelon Research, and approximately 7% of USA population (21 million) are actively enrolled.

¹⁰ Approximately 21% of USA population (70 million) have ever been recorded by ORD, and approximately 4% of USA population (13 million) are actively enrolled.

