9.7 Data Analysis

All data analysis will be performed separately for each data source on the study population as defined in Section 9.2.2. The study population selection process will be reported using a STROBE

(STrengthening the Reporting of OBservational studies in Epidemiology) diagram that shows cohort and sub-population exclusions step by step, as defined in Section 9.2.2.

All study results will be presented separately for each data source in the study reports, as appropriate when data become available. The full study reports for all data sources, including all descriptive, comparative, exploratory, and sensitivity analyses, as well as the meta-analysis results will be provided in the final report. The study reporting is described in detail in Section 6.

A full description of the analytical approach will be developed and described in the SAP. Also details on data derivations, category definitions, analyses, and presentation of the study results will be provided in SAP. The SAP will be finalised prior to the conduct of the study analyses.

In this study, the missing data will be reported as part of descriptive analysis (see Section 9.7.1). Methods commonly used in non-interventional studies for handling missing data, such as imputation, complete case analysis or indicator for missing values, will be considered (35). The SAP will describe the full details on handling missing data that will include the methods for identifying where missing data methods should be applied, the techniques for identifying the type of missing information and the appropriate imputation methods to be used, if any.

The small number masking rules define the lower limit for the number of units that can be reported in a table. The small number masking rules vary by data sources. For example, Denmark and Finland have a limit of 5, USA (Carelon Research) has a limit of 10 and France has a limit of 11. The small number masking rules of the data sources will be considered when presenting the study results for descriptive and comparative analysis. If the small number masking rules apply, only the comparative analysis results for the relevant study outcome (and no descriptive analysis results for the relevant study outcome) will be provided to avoid inadvertent unmasking of small numbers.

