In the descriptive analysis, the total number of patients at risk and the number of events for each study outcome in the study sub-cohorts (exposed to anifrolumab and unexposed to anifrolumab as defined in Section 9.2.2) will be tabulated before and after application of PS adjustment, if suitable for the data. The measures of study outcomes will be estimated before and after application of PS adjustment (if suitable for the data) to obtain crude and adjusted estimates, respectively. The measures of study outcomes, with associated 95% CIs, will be estimated for the study sub-cohorts exposed to anifrolumab and unexposed to anifrolumab as defined in Section 9.2.2. In this study, cumulative incidence (i.e. incidence proportion) by exposure status to anifrolumab during pregnancy will be assessed for the following study outcomes: MCM (objective 1 & 15), select pregnancy loss outcomes (composite of spontaneous abortion and stillbirth) (objective 3 & 13), mCM (objective 6), adverse pregnancy outcomes (objective 8), adverse birth outcomes (objective 10), and adverse outcome related to infant growth up to one year of age (objective 12).

Additionally, the description of the time from birth to MCM ascertainment will be conducted in live and non-live offspring from women who had moderate/severe SLE and were exposed or unexposed to anifrolumab during the first trimester of pregnancy. The time to MCM ascertainment will be calculated from birth and up to 1 year after birth. The time to MCM ascertainment will be estimated both before and after application of PS adjustment (if suitable for the data) to obtain crude and adjusted estimates, respectively. Kaplan-Meier curves (and their 95% CIs) will be used for characterising the time from birth to MCM ascertainment. Together with the Kaplan-Meier curves, the number of patients at risk at appropriate time intervals (e.g., 7 days or as seen appropriate for the study), and the median (with 95% CI) for the time from birth to MCM ascertainment will be reported.

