9.7.3 Secondary objectives

The analysis for the secondary study objectives will be conducted separately for each data source. The description of the analysis to be conducted for each secondary study objective is provided in the following sections.

Objective 5

To describe the demographic and clinical characteristics of the live and non-live offspring and their mothers who had moderate/severe SLE and were exposed or unexposed to anifrolumab during the first trimester of pregnancy or anytime during pregnancy (study objective 5), the descriptive analysis of the demographic and clinical characteristics (as defined in Section 9.3.3) will be provided as described Section 9.7.1. The demographic and clinical characteristics of the

live and non-live offspring and their mothers will be presented separately for each study cohort and sub-cohorts as defined in [Table 5](#) (Section [9.2.2](#)). No statistical testing comparing the distribution of demographic and clinical characteristics distribution between the study cohorts or sub-cohorts is planned.

Objective 6

The analysis to describe and estimate the risk of mCM in live and non-live offspring from the mothers with moderate/severe SLE who were exposed or unexposed to anifrolumab during pregnancy (study objective 6) will be performed using the *mCM* cohort and its sub-cohorts as defined in Section [9.2.2](#). The crude and adjusted cumulative incidence (with corresponding 95% CI) of the mCM in live and non-live offspring from the mothers will be estimated separately for the case where mother had moderate/severe SLE and was exposed or unexposed to anifrolumab during pregnancy. The crude cumulative incidence (i.e., risk) will be calculated as the total number of live and non-live offspring with mCM divided by the total number of live and non-live offspring. The adjusted cumulative incidence (i.e., risk) will be estimated following PS adjustment described in Section [9.7.1](#).

Objective 7

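### Objectives 1 and 6 take the crude malformation risk over all offspring, so live-born infants who leave the data uncoded before one year count as unaffected; the crude risk is slightly understated

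*Protocol*

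**What the plan says.** - **Risk formula.** For MCM (9.7.2, Objective 1): "The crude cumulative incidence (i.e., risk) will be calculated as the total number of live and non-live offspring with MCM divided by" all live and non-live offspring. For mCM (9.7.3, Objective 6): "total number of live and non-live offspring with mCM divided by the total number of live and non-live offspring".
- **Window.** For live births, MCM is ascertained from birth to one year (9.3.2); 9.1 gives the same window for mCM.
- **End of follow-up.** For MCM, 9.3.2 ends follow-up at the first of several events, including emigration and "loss to follow-up (disenrollment/de-registering), reaching the age of 1 year or date of first diagnosis of the outcome at study". For mCM it repeats the rule: "loss to follow-up (disenrollment/de-registering), reaching the age of 1 year or date of first diagnosis of the outcome at study, whichever is the soonest".
- **Cohort entry.** For offspring other than recorded losses and terminations, Table 5 (9.2.2) asks for "Pregnancies with linkage mother-offspring within the study time period". It sets no infant enrolment period. The 12-month enrolment rule applies to the mother, before LMP2.
- **Time-to-event description.** Section 9.7.1 and Objective 1 plan crude and PS-adjusted Kaplan-Meier curves of time from birth to MCM ascertainment, with "the number of patients at risk at appropriate time intervals (e.g., 7 days or as seen appropriate for the study"). No such curve is planned for mCM.
- **Masking.** Under 9.7, "USA (Carelon Research) has a limit of 10 and France has a limit of 11". Where a limit applies, only the comparative result is shown for that outcome.

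**The concern.** The follow-up rule and the risk formula treat the same infant differently. Under 9.3.2, an infant who disenrols at two months without a code is censored at two months. Under Objectives 1 and 6, that infant stays in the denominator as if observed unaffected for the full year. A malformation coded later under another insurer is lost from the numerator.

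The direction of the error is known: it lowers an absolute malformation risk in a safety study. It matters mainly in Carelon and DAPI, where observation depends on insurance enrolment. In France people leave the data only at death or emigration (9.4.1.3). The protocol fixes this numerator and denominator itself, so the formula is not a detail left to the SAP. The PS-adjusted risk is not fixed in the same way, and the point does not extend to it.

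**Working it through.** **The plan's own figures.** At 10% uptake and 7% risk, expected exposed MCM cases are 102 × 0.07 = 7.14 (Carelon), 114 × 0.07 = 7.98 (DAPI) and 116 × 0.07 = 8.12 (France). Table 11 shows 7, 7 and 8, so the decimals are dropped. Simulating the method of 9.5.1.3 gives power of 96.1% (1:2) and 98.2% (1:3), against 96% and 98% in Table 13. None of this is in dispute.

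**Does another provision remove the problem?**
- The early last-inclusion date in Table 4 deals with administrative censoring only.
- The missing-data paragraph in 9.7 leaves methods to the SAP but does not alter the stated denominator.
- Section 9.9 discusses imperfect outcome capture in general, without naming disenrolment.
- The Kaplan-Meier curves are additional to the stated risk and cover MCM only.

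**Turnover (assumption).** The protocol gives no infant disenrolment rate. Table 8, footnote 9, states: "20% of USA population (75 million) have ever been recorded by Carelon Research, and approximately 7% of USA population (21 million) are actively enrolled". Footnote 10 gives 70 million ever recorded and 13 million active for Optum. Assume stable plan size, no returns, infants leaving like other members, and counts taken at mid-2022. The annual exit rate is then h = (ever/active − 1)/years.

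| Source and start year | h | Leave within 1 year, 1 − e^(−h) | Mean share gone at a diagnosis spread evenly over the year, 1 − (1 − e^(−h))/h |
|---|---|---|---|
| Carelon, 2006 | (75/21 − 1)/16.5 = 0.156 | 0.144 | 0.074 |
| Optum, 1994 (9.4.1.5) | (70/13 − 1)/28.5 = 0.154 | 0.143 | 0.073 |
| Optum, 2007 (Table 8) | (70/13 − 1)/15.5 = 0.283 | 0.246 | 0.129 |

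**Live share of the MCM cohort.** With 20% non-live births and linkage of 73% and 85% (9.5.1.2): Carelon 0.584/0.784 = 0.745; DAPI 0.680/0.880 = 0.773.

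**Missed share of MCMs.** This is (1 − q) × share gone × live share. Here q is the share of live-born MCMs coded at birth, assumed to be 0.9 to 0.5, with the rest spread evenly over the year.
- Carelon: 0.0055 to 0.0276, so 7.0% is reported as 6.96% to 6.81%.
- DAPI: 0.0057 (q = 0.9, 1994 start) to 0.0498 (q = 0.5, 2007 start), so 6.96% to 6.65%.
- Exposed US cases missed: 0.04–0.20 plus 0.05–0.40, or 0.08 to 0.60 of 15.1.
- 95% half-width, 1.96 × √(0.07 × 0.93/n): 4.95 points (n = 102) and 4.68 points (n = 114).

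**Harsher case.** Suppose 30% of all offspring leave and half of MCMs are coded at birth. Exits spread over the year give 7 × 0.925 = 6.48%; exits about one month after birth give 7 × 0.8625 = 6.04%. In a simulation with 30% leaving evenly over the year, the crude proportion was 6.44% and one minus Kaplan-Meier was 6.97%. The censoring-aware estimate therefore recovers the 7%.

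**Risk ratio.** Under equal loss the bias factor is 1.00. The unequal cases use q = 0.5 and a US live share of 0.760, and pool with unaffected France at a US weight of 216/332.
- Annual exit rates of 0.283 v 0.154: 0.98 or 1.02 within a US source, by direction; 0.99 or 1.01 pooled.
- Assumed 30% v 10% leaving: 0.96 or 1.04 within a US source; 0.97 or 1.03 pooled.

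**Masking.** P(Bin(102, 0.07) < 10) = 0.82 for Carelon; P(Bin(116, 0.07) < 11) = 0.81 for France.

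**The case against.** The strongest reply is that this does not matter. The shift is at most about a third of a point under the turnover assumptions, a small fraction of the half-width. For MCM, Objective 1 already yields a censoring-aware live-birth curve with numbers at risk, so the argument is partly about which figure is called the risk. Both points stand, and they hold the severity to minor. They leave the wrong figure as the stated risk, and they do not cover mCM.

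A second reply is that an infant who leaves uncoded is simply a missed case, and 9.9 admits imperfect sensitivity. That is fair as disclosure. But this part of the under-ascertainment can be corrected from exit dates that the study already derives.

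The magnitude inputs are also weak. Infants linked to mothers with at least 12 months of enrolment may be more stable than average members. The Optum rate nearly doubles with the start year, and the coded-at-birth range has no source in the protocol. The figures show an order of magnitude only.

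Finally, masking will probably withhold Carelon's descriptive MCM result, so the crude-risk problem may fall mainly on DAPI. The same rule may suppress some of the tables proposed here.

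A reader might infer that the MCM risk ratio, and so the case against a ratio of 2.5, is compromised. The documents do not support that. Nothing in them suggests that leaving differs by exposure, and even the assumed 30% v 10% split moves the pooled ratio by about 3%.

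**Conclusion.** The point holds and is minor. Objectives 1 and 6 define a crude one-year risk that counts infants who leave early as unaffected. For MCM, a true 7.0% would be reported as about 6.96% to 6.81% in Carelon and 6.96% to 6.65% in DAPI. This rests on the assumed turnover, on 50% to 90% of live-born MCMs being coded at birth, and on even timing of the rest; earlier or heavier exit would enlarge the shift. The mCM bias has the same direction, but the protocol gives no baseline from which to size it.

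It would go too far to say that the plan ignores censoring: for MCM the planned curves contain the live-birth figure needed, though they are not the stated risk. For mCM nothing equivalent is planned.

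**What to change.** 1. In Objectives 1 and 6, define the crude risk for live births as the one-year cumulative incidence with censoring at disenrolment or emigration. Non-live offspring contribute their status at end of pregnancy. Add an mCM curve.
2. Tabulate disenrolment before one year by exposure group and data source, where masking allows.
3. Keep the planned risk-ratio model as primary. If a sensitivity analysis for early exit is added to 9.7.5, use inverse-probability-of-censoring weights or a ratio of censoring-aware risks.

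Do not restrict to offspring observed to one year, malformation or death. That keeps cases who later leave and drops non-cases who leave. With the inputs above, the restricted risk would be 7.6% to 7.7% in Carelon and 7.6% to 8.4% in DAPI, a larger error than the one being corrected. With 30% of exposed and 10% of unexposed infants leaving and a true ratio of 1, the restricted ratio within a US source would be 1.14 to 1.17, against 0.96 to 0.99 as planned.

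The cost is small: rewording two objectives, one extra curve, one table and possibly one sensitivity analysis, using exit dates already required. The downside is slightly wider intervals and a little more analysis work.
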